## 1.0 PROTOCOL SUMMARY AND/OR SCHEMA

Translational studies in analgesic pharmacology: analgesic synergy in clinical pain. A phase 2 study comparing a single dose of a 1:1 combination of methadone and morphine with morphine alone in patients with post-operative pain.

The objective of this proposal is to compare the analgesic effects of a combination of morphine and methadone with morphine alone to determine synergistic activity of mu opioid analgesics in humans.

This is a randomized, double blind, parallel arm study (See Appendix 1).

We will administer a single dose of 1 mg of IV methadone plus 1 mg of morphine or 2 mg of IV morphine to patients one day after retroperitoneal lymph node dissection. We are planning for 70 patients to complete the study, 35 in each group.

All patients will receive Patient Controlled Analgesia (PCA) with IV morphine. The total amount of opioid available to patients will be equivalent to the standard amounts used after retroperitoneal lymph node dissection. Informed consent will be obtained from all patients pre-operatively. The PCA settings will start after the surgery at 1 mg/hour continuous infusion and 1mg every 10 minutes as needed. Clinician activated boluses (CAB) of morphine 5 mg IV will be available to the patient. The day after the surgery, the PCA will be stopped for the period of the study and we will ask the patient to request pain medication as soon as he feels at least moderate pain. During the period of the trial the physician will have no other clinical or other responsibilities. A physician will be available to monitor the time to the patient's request for pain medications, assess pain intensity and administer the drugs to replace the PCA promptly upon the patient's request. No more than 2 patients per the doctor per floor will be enrolled on the same day. When the patient requests pain medication, baseline pain intensity will be assessed and open label 2 mg of morphine administered. After administration of morphine the patient's pain relief, pain intensity, and side effects reported by the patient will be assessed every 10 minutes, and/or at the time the patient requests analgesia medication. In addition, respiratory rate will be recorded during these intervals. Immediately upon the second request for analgesia, the study drug in a double blind fashion (1 mg of IV methadone plus 1 mg of morphine or 2 mg of IV morphine), will be administered by the doctor. After administration of the study drug, pain relief, pain intensity, side effects reported by the patient and respiratory rate will be assessed every 10 minutes, and/or at the time the patient requests analgesia medication. Upon the third request for analgesia medication the study is completed, and the PCA will be restarted at the pre-study dose. We will also collect information about the total dose of morphine received while on IV PCA, the dose of morphine received during the last hour before stopping the PCA, and the time from stopping PCA to first request for analgesic medication.

**Memorial Sloan-Kettering Cancer Center  
IRB Protocol**

**IRB#: 05-025A(7)**

Morphine 2 mg intravenously will be administered upon the first request for an analgesic medication. Upon the second request, depending on the randomization, the patient will receive morphine 2 mg intravenously or a combination of morphine 1 mg and methadone 1 mg intravenously. There will be no dose escalation.

	Upon the 1st Request for Analgesic Medication	Upon the 2nd Request for Analgesic Medication
Randomized to Group 1	morphine 2 mg	morphine 2 mg
Randomized to Group 2	morphine 2 mg	morphine 1 mg and methadone 1 mg

**2.0 OBJECTIVES AND SCIENTIFIC AIMS**

- The objective of this study is to compare the analgesic effects of a combination of morphine and methadone with morphine alone to determine synergistic activity of mu opioid analgesics in humans.

**3.0 BACKGROUND AND RATIONALE**

Much is known about basic mechanisms of nociception and analgesia in animal models of experimental pain (1). Very few of these basic mechanisms, however, have been confirmed in humans suffering clinical pain (2). A better mechanistic classification of clinical pain syndromes offers the possibility of improved analgesic therapies and more rational drug development strategies (3,4).

Biochemical and functional characterizations of mu receptor subtypes have been accomplished in the laboratory, but the specific pharmacological profiles of mu opioid receptor subtypes have not been confirmed in clinical pain studies. For example, animal models reveal incomplete cross-tolerance among many mu opioids (5-9). In the treatment of cancer pain, clinicians commonly switch a patient who is highly tolerant to one mu selective opioid to another mu selective opioid in a process termed “opioid rotation” (10-11). Switching the patient to a different opioid often restores analgesia at a lower dose. This incomplete cross-tolerance suggests that drugs previously classed as “mu selective” may actually be acting via different mu receptor subtypes. At our institution, pain specialists sometimes add methadone to the regimen of patients on high doses of other opioids in an attempt to forego the need for a new increase in opioid dose. These clinical attempts to take advantage of the incomplete cross tolerance and possible synergy among different opioids have not been studied, and their efficacy is therefore unknown.

**Memorial Sloan-Kettering Cancer Center  
IRB Protocol**

**IRB#: 05-025A(7)**

We have obtained experimental data that demonstrate a profound analgesic synergy between morphine and methadone when co-administered systemically in mice [see *data*] (12).

If this type of synergy can be demonstrated in clinical pain, it will be a relatively unique example of translating concepts of fundamental aspects of opioid actions seen in the laboratory to the clinical area, and provide a basis for offering new and scientifically-based analgesic regimens. This may provide better pain relief with less opioid related side effects in clinical practice.

While studying the potency of methadone in single dose studies, its analgesic potency was found to be equivalent to the potency of morphine when the drugs were administered parenterally (13).

A double-blinded investigation was performed to assess pain scores and opioid requirements in the first 24 hours post-operatively after the same doses of morphine and methadone (0.3 mg/kg) was administered intra-operatively parenterally as a single dose. No difference in the amount of analgesic requirements post-operatively or the visual analogue scale pain score was observed between the group that received morphine and the group that received methadone (14).

In another double-blind study, morphine and methadone efficacy was examined in a post-operative pain control model. Patients in each group received a 20-mg dose of the opioid (morphine or methadone) intra-operatively. Rescue doses of the same opioid were available. There was no significant difference in the amount of supplementary opioid requirements between the two groups in the immediate post-operative period (about 8 hours) (15).

The third double-blind randomized trial compared post-operative analgesia after peri-operative loading doses of methadone and morphine. Methadone or morphine, 0.25 mg/kg, was given intravenously at induction of anesthesia and rescues were administered in the recovery room. The mean analgesic doses of morphine and methadone were similar (0.43 mg/kg and 0.45 mg/kg, respectively), with no significant difference in pain control or opioid requirements between the two groups in the post-operative period (about 12 hours). After 12 hours, the group receiving repeated administration of methadone had lower pain scores and less supplementary opioid requirement (16).

These studies support the equianalgesic effect of morphine and methadone when administered as single doses parenterally in the post-operative pain model in humans. We conclude that to evaluate synergy, we need to conduct a single dose study to avoid the confounding effects of methadone accumulation.

Memorial Sloan-Kettering Cancer Center  
IRB Protocol

IRB#: 05-025A(7)

**Pre-clinical data:**

The proposed clinical study is based on the following experimental studies.

*Methods:*

In these studies, analgesia was measured in mice 30 min post-injection (unless otherwise stated) using the radiant heat tail-flick assay (12). Baseline latencies ranged between 2.0 and 3.2 sec. A maximal cutoff latency of 10 sec was set to minimize tissue damage. Analgesia was assessed quantitatively as a doubling or greater of the baseline latency for each mouse. Drugs were administered systemically via subcutaneous injections. Groups of mice were compared using the Fisher Exact Test. ED50 values and 95% confidence limits were calculated by the Litchfield-Wilcoxon method.

Synergy was evaluated using isobolographic analysis. Significance was defined as the lack of overlap of 95% CL for the predicted and observed analgesia.

[figure not shown]
To examine the gastrointestinal transit immediately after subcutaneous (s.c.) injection, mice received a per os (p.o.) charcoal meal (10% charcoal with 2.5% gum tragacanth, w/v). Thirty minutes after the charcoal meal, the animals were sacrificed by cervical dislocation and the distance the meal traveled was measured.

*Results:*

The analgesia provided by the combination of morphine and L-methadone (73%) is significantly greater than the sum of their independent actions (20%),  $P < .001$ . The interaction of the morphine metabolite M6G with L-methadone (60%) is three times greater than the additive effect of the two drugs (20%;  $P < .001$ ) (Fig. 1A and 1B).

Figures 1A and 1B.

[figure not shown]

The interactions of oxymorphone, oxycodone, fentanyl, alfentanil, meperidine and [Dmt1]-DALDA with L-methadone were shown to be additive and not synergistic (Fig. 1A). The same compounds were also co-administered with morphine, but no statistically significant synergistic interactions were found (Fig. 1B).

The ED50 values of morphine and L-methadone administered individually were 3.8 mg/kg (2.6, 5.4) and 1.9 mg/kg (1.4, 2.4), respectively. However, when co-administered, the ED50 of the morphine/L-methadone combination is 0.52/0.26 mg/kg (0.35, 0.8; 0.17, 0.4), 3.5 times less than their ED50 values when administered individually. Isobolographic analysis of this interaction indicates synergistic interactions between morphine and L-methadone; the ED50 of the combination of drugs falls below the line of additivity of the two individual ED50 values (Fig. 2A).

Figure 2.

[figure not shown]

As an example of isobolographic analysis of a drug combination where synergy is not present, fentanyl and L-methadone are shown (Fig. 2E). Administered individually, fentanyl has an ED50 value of 0.25 mg/kg (0.013, 0.03). When administered with L-methadone, the ED50 value is 0.011/0.9 mg/kg (0.0058, 0.015; 0.015, 1.2) When plotted on the isobole, this ED50 value falls along the line of additivity and is therefore not considered synergistic. Fentanyl and alfentanil were given twenty minutes post L-methadone injection (ten minutes prior to testing) in order for the peak effects to coincide.

Synergy seen between L-methadone and morphine was restricted to analgesia and did not extend to other mu opioid receptor actions, such as gastrointestinal transit.

Figures 3A and 3B.

Morphine decreased gastrointestinal transit relative to saline treated animals ( $28.1 \pm 1.5$  cm) by 26% ( $20.7 \pm 1.9$  cm) at the 0.5 mg/kg dose. Gastrointestinal transit was reduced by 36% ( $18 \pm 1.9$  cm) in the 0.25 mg/kg L-methadone treated animals. When we administered the combination of morphine and L-methadone (0.5 and 0.25 mg/kg, respectively), transit was inhibited by 42% ( $16.2 \pm 1.9$  cm). The expected additive effect of the combination of morphine and L-methadone would be an inhibition of 62.5%. Morphine and L-methadone, when co-administered in the gastrointestinal transit assay did not therefore exhibit a synergistic side effect (Fig. 3B). This is in contrast, therefore, to the effect seen with the same doses of morphine and L-methadone when co-administered in the tail-flick assay, where a profound analgesic synergy is observed (Fig. 3A). Both analgesia and gastrointestinal transit are mu receptor actions and are readily reversed by naloxone.

#### Conclusion:

These animal experiments demonstrate synergistic analgesic effects between some mu opioid agonists such as morphine and methadone, but not others such as methadone and fentanyl. The finding of enhanced analgesia without enhanced bowel dysmotility also demonstrates an interesting dissociation of mu opioid actions. Furthermore, the lack of synergy in inhibition of gastrointestinal transit suggests that co-administration of morphine and methadone to patients will result in increased analgesia without worsening constipation and, therefore, may constitute a useful strategy in the treatment of pain.

## 4.0 OVERVIEW OF STUDY DESIGN/INTERVENTION

### 4.1 Design

This is a randomized, double blind, parallel arm study. We will administer a single dose of 1 mg of IV methadone plus 1 mg of morphine or 2 mg of IV morphine to patients one day after surgery (See Appendix 1).

## 4.2 Intervention

All patients will receive Patient Controlled Analgesia (PCA) with IV morphine as per routine post-operative analgesic care. The total amount of morphine available to patients will be equivalent to the standard amounts used after surgery. Informed consent will be obtained from all patients pre-operatively. The PCA settings will start in the recovery room at 1 mg/hour continuous infusion and 1mg every 10 minutes as needed, clinician activated boluses will be available, and the PCA will be titrated to pain control as needed.

The day after the surgery, the PCA will be stopped temporarily, and we will ask the patient to request pain medication as soon as he feels at least moderate pain (See Appendix 1). If two hours pass before a first request for pain medication is made, the patient will be removed from the protocol. During the period of the trial the doctor will have no other clinical or other responsibilities. A doctor will be available to monitor the time to the patients' request for pain medications, assess pain intensity and administer the drugs to replace the PCA promptly upon the patient's request. No more than 2 patients per doctor per floor will be enrolled on the same day.

Upon the first request for analgesia, immediately before administration of morphine 2 mg and every 10 minutes after administration of morphine 2 mg, we will record the patient's pain relief, pain intensity, respiratory rate, and side effects as reported by the patient. If four hours pass before a second request for pain medication is made, the patient will be removed from the protocol.

Upon the second request for analgesia, immediately before administration of the blinded study drug (1 mg of IV methadone plus 1 mg of morphine or 2 mg of IV morphine), every 10 minutes thereafter, and at the time of the third request for analgesia, we will record the patient's pain relief, pain intensity, respiratory rate, and side effects as reported by the patient.

Upon a third request for analgesia, the study is completed and the PCA will be restarted at the pre-study dose. If four hours pass before a third request for pain medication is made, the patient will be removed from the protocol.

## 5.0 THERAPEUTIC/DIAGNOSTIC AGENTS

Morphine, a phenanthrene derivative, is the prototype opioid agonist. All other opiates are compared to morphine in determining their relative analgesic potency. Because of its widespread availability, it is the drug of choice for the treatment of post-operative pain and severe pain associated with cancer (17). There is no ceiling to its analgesic effect, although side effects, particularly sedation, respiratory depression and confusion may intervene before optimal analgesia is achieved (18, 19). It is metabolized in the liver, where it undergoes glucuronidation at the 3 and 6 positions. In single dose studies it is equipotent to methadone (20). The duration of analgesia is 3-4 hours. Because of the low dose used, we do not expect

**Memorial Sloan-Kettering Cancer Center  
IRB Protocol**

**IRB#: 05-025A(7)**

significant side effects in patients who have been already receiving morphine for over 12 hours.

Methadone, the 50/50 racemic combination of d-methadone and l-methadone, has been in widespread use for decades and has been studied extensively. There is no evidence of organ toxicity from chronic opioid use, including chronic methadone use (21). The main concern when using methadone for the treatment of pain is its long and unpredictable half-life which, with chronic administration, is associated with the risk of delayed opioid toxicity with side effects such as sedation, confusion and respiratory depression. For this reason methadone is generally viewed as a second line opioid, generally used after other opioids with a more predictable dose-response have been tried. This is a single dose study and therefore drug accumulation will not occur. Because of the low dose used, we do not expect toxic effects or significant side effects in patients who would be receiving morphine for over 12 hours by the time the study begins.

Preservative-free methadone and morphine combination (1 mg morphine+1 mg methadone) and parenteral morphine (2 mg of morphine IV) will be prepared, vialled and blinded by the MSKCC pharmacy. The methadone injection will be provided in single use vials containing 1 mg/ml, 0.5 ml, or 1 mg/ml, 2 ml. The morphine injection will be provided in vials containing 5 mg/ml, 1ml. Morphine and methadone are compatible for 7 days. Drugs will be dispensed by the pharmacy to the clinical investigator in a blinded fashion on the day of the study.

## **6.0 CRITERIA FOR SUBJECT ELIGIBILITY**

Planned retroperitoneal lymph node dissection usually requiring post-operative analgesia with PCA at 1 mg continuous infusion and 1 mg every 10 minutes as needed (See Appendix 2).

### **6.1 Subject Inclusion Criteria**

- Retroperitoneal lymph node dissection
- Planned post-operative analgesia with PCA at 1 mg continuous infusion and 1 mg every 10 minutes
- 18 years of age or older
- English-speaking
- Give informed consent to participate in this study

## 6.2 Subject Exclusion Criteria

- Known hypersensitivity to methadone or morphine
- Patients with past or present history of substance abuse
- Patients with a history of methadone treatment
- Patients with a history of chronic pain requiring daily analgesic use for more than 3 months
- Patients treated with opioids within one month from the scheduled surgery
- Creatinine clearance less than 50 mg/kg (using Cockcroft-Gault Equation).
- Neurologic or psychiatric disease sufficient, in the doctor's opinion, to compromise data collection

## 7.0 RECRUITMENT PLAN

Patients will be recruited in the pre-operative period.

## 8.0 PRETREATMENT EVALUATION

Demographic (age, ethnicity) and clinical data, including weight, height, past medical and surgical history, past treatment with opioids, concurrent drug therapies, drug-related side effects, and serum creatinine clearance within one month of surgery will be collected (See Appendix 3). We will also collect the data on the total dose of morphine received while on IV PCA, dose of morphine received during the last hour before stopping the PCA, and the time from stopping the PCA to first request for analgesic medication (See Appendix 4).

## 9.0 TREATMENT/INTERVENTION PLAN

We will administer a single dose of 1 mg of methadone with 1 mg IV of morphine or 2 mg of IV morphine alone to patients the day following surgery.

Following surgery, all patients will receive Patient Controlled Analgesia (PCA) with IV morphine. As per post-operative standard care, the PCA settings will start at 1 mg/hour

**Memorial Sloan-Kettering Cancer Center  
IRB Protocol**

**IRB#: 05-025A(7)**

continuous infusion and 1mg every 10 minutes as needed and titrated up as needed. CABs as needed will be available (See Appendix 1).

The day after the surgery the PCA will be stopped for the period of the study. We will ask the patient to request pain medication as soon as he feels moderate pain. The doctor will be present to monitor the time of the patient's request, assess pain intensity and administer drugs to replace the PCA promptly upon the patient's request. If two hours pass before a first request for pain medication is made, the patient will be removed from the protocol. Not more than two patients per doctor per floor will be enrolled on the same day. During the period of the trial, the doctor will have no clinical or other responsibilities.

1. When the patient requests pain medication, baseline pain intensity will be assessed and open label 2 mg of morphine IV administered. After administration of morphine, the patient's pain relief, pain intensity, respiratory rate, and side effects reported by the patient will be assessed every 10 minutes, and at the time of the second request for analgesia medication. If four hours pass before a second request for pain medication is made, the patient will be removed from the protocol.

2. Immediately upon a second request for analgesia, the study drug in a double blind fashion (1 mg of methadone IV plus 1 mg of morphine IV or 2 mg of morphine IV), will be administered by the doctor. After administration of the study drug, the patient's pain relief, pain intensity, respiratory rate, and side effects reported by the patient will be assessed every 10 minutes, and at the time of the third request for analgesia medication.

3. Upon a third request for analgesia medication or after four hours if no medication is requested, the study is completed and the PCA will be restarted at the pre-study dose. If four hours pass before a third request for pain medication is made, the patient will be removed from the protocol.

The total amount of opioid available to patients will be equivalent to the standard amounts used after retroperitoneal lymph node dissection.

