**IRB#: 05-025A(7)**

- Pain relief scores on a 0-100% scale
- Pain intensity scores on a 0-10, 11 point, verbal scale
- Respiratory rate
- Side effects from the pain medication and their severity rated by the patient on a 0-3 scale (none, mild, moderate, severe)
- Time to the second request for the pain medication
- Global assessment. The patients will be asked: "How effective was the medication in relieving your pain?" The patient will choose among: 1) not effective 2) slightly effective 3) moderately effective 4) very effective 5) extremely effective.

Immediately before administration of the study drug, i.e. morphine 2 mg IV or morphine 1 mg with methadone 1 mg IV, every 10 minutes and at the time of the third request for analgesia, we will record (See Appendix 5):

- Pain relief scores on a 0-100% scale
- Pain intensity scores on a 0-10, 11 point, verbal scale
- Respiratory rate
- Side effects from the pain medication and their severity rated by the patient on a 0-3 scale (none, mild, moderate, severe)
- Global assessment. The patients will be asked: "How effective was the medication in relieving your pain?" The patient will choose among: 1) not effective 2) slightly effective 3) moderately effective 4) very effective 5) extremely effective.
- Time to the third request for the pain medication (upon which the study is completed)

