### 14.0 BIostatISTICS

The primary comparison will be the difference in pain relief recorded as the "area under the curve" (AUC) between the initial 2 mg morphine dose and the study drug. AUC will be estimated by plotting % of pain relief over the time (see Appendix 6).

Time (t) for each AUC will include:

For area A:

- t0, time of the first request for the analgesia and opened administration of 2 mg morphine;
- t2, 3, ..., time of assessments 10 minutes apart
- tn, time of the second request for analgesic medication and study drug administration.

For area B:

- t0 time of the second request for analgesic medication and study drug administration;
- t2, 3, ..., time of assessments 10 minutes apart;
- tn, time of the third request for analgesic medication and completion of the study.

Pain relief at the time of the request for pain medication will be considered baseline and each patient will serve as his own control. Should the pain relief score at the time of the second pain medication administration be reported higher than the baseline, projected AUC will be used, extending it to the baseline.

AUC for 2 mg morphine (area B1) and AUC for a combination of 1 mg morphine and 1 mg methadone (area B2) will be compared to the AUC for open label 2 mg morphine (area A).

**Memorial Sloan-Kettering Cancer Center  
IRB Protocol**

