**IRB#: 05-025A(7)**

If the true difference between mean ratio B/A for morphine plus methadone vs morphine alone is .68 times the within-group standard deviation, then with 35 patients completing the study per arm there would be an 80% chance of a significant comparison with a two-sided t-test at  $p < 0.05$ .

The main analysis will be the analysis of covariance, using baseline pain as a covariate, and analyze time-to-first-rescue (the time from stopping PCA to first request for analgesic medication), and changes in pain intensity as secondary outcomes. We will also collect the information about the total dose of morphine received while on IV PCA and the dose of morphine received during the last hour before stopping the PCA and the time from stopping PCA to first request for analgesic medication to stratify subjects during analysis.

We are planning to review the data after 10 cases and may need to adjust the dose of morphine as well as morphine and methadone accordingly, by doubling the dosage. With the change of the dose, a new patient accrual will be started. The data for the initial opioid dose will be analyzed separately.

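### The only pain-intensity score called baseline precedes the open-label dose; Section 14.0 should add the score taken just before the blinded drug as a covariate and measure change from it

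*Combined protocol and SAP*

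**What the plan says.** **Where the label is attached.** Section 9.0, item 1, reads "When the patient requests pain medication, baseline pain intensity will be assessed and open label 2 mg of morphine IV administered". Section 1.0 says the same of the first request: "baseline pain intensity will be assessed and open label 2 mg of morphine administered". No other section calls a pain-intensity score baseline.

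**Where the term is used.** Section 14.0 states: "The main analysis will be the analysis of covariance, using baseline pain as a covariate". It is the only covariate named for that model. The same sentence lists "changes in pain intensity as secondary outcomes". Neither phrase comes with a time point, and the covariate has no stated scale.

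**A second use of the word.** Section 14.0 also says "Pain relief at the time of the request for pain medication will be considered baseline and each patient will serve as his own control". This concerns pain relief, not intensity, and does not say which request is meant. The projection rule that follows begins "Should the pain relief score at the time of the second pain medication administration be reported higher than the baseline", which compares a second-request score with an earlier one.

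**The score just before the randomised drug.** It is collected. Section 4.2 schedules an assessment "Upon the second request for analgesia, immediately before administration of the blinded study drug", and Section 10.0 does so "Immediately before administration of the study drug, i.e. morphine 2 mg IV or morphine 1 mg with methadone 1 mg IV". Both include pain intensity, and Assessment Form 2 (Appendix 5) has a field for it at the second request. None of these places calls it baseline.

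**The concern.** Both arms receive open-label morphine at the first request. The arms differ only from the second request, which may come up to four hours later (Sections 4.2 and 9.0). An analyst who looks up what the protocol means by baseline pain intensity will find the first-request score.

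Two things are at stake. First, the main analysis would adjust only for pain at the start of area A and leave out pain at the start of area B, although the primary outcome is the ratio B/A. Second, a change in pain intensity measured from the first request would add the response to the open-label dose to the response to the study drug. A reader of the within-arm results could credit the blinded drug with relief that came before it.

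**Working it through.** **1. The plan's own figure.** Inputs from Section 14.0: 35 completers per arm, a difference of 0.68 within-group SD in mean B/A, and a two-sided t-test at 0.05. The noncentrality is 0.68 × √(35/2) = 2.84 on 35 + 35 − 2 = 68 degrees of freedom, which gives 80.1% power (81.2% by normal approximation). The stated 80% is reproduced. No baseline score enters it, so the definition of baseline cannot change it.

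**2. Validity of either covariate.** The randomisation code is generated after consent, before surgery (Sections 4.2 and 15.2). Both scores come after assignment but before the blinded drug, so the drug cannot have affected them. A simulation of 20,000 complete trials with 35 per arm assumed correlations of 0.3 (first-request score with outcome), 0.5 (second-request score with outcome) and 0.5 (between the two scores). ANCOVA on the first- or the second-request score gave type I error of 4.9% or 5.1%. The mean estimate was 0.680 with either, against a true 0.68. I use this run only to show validity: any difference in precision in it comes from the correlations put in.

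**3. Precision for B/A.** Write P1 and P2 for first- and second-request pain, each with unit variance and correlation ρ. As an assumed model, log A = −bP1 + e and log B = −bP2 + e′, where e and e′ are independent with variance s². Then log(B/A) = b(P1 − P2) + (e′ − e).

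- cov(P1, log B/A) = b(1 − ρ) and cov(P2, log B/A) = −b(1 − ρ). Either score alone explains b²(1 − ρ)².
- Both together explain var[b(P1 − P2)] = 2b²(1 − ρ).
- With ρ = 0.5: either alone explains b² × 0.25 = 0.25b²; both explain 2b² × 0.5 = 1.00b².
- Residual variance is 2s² with both scores and 2s² + b²(1 − ρ²) with one. The ratio of the first to the second is 1 when b = 0 and falls towards 0 as b²/s² grows.

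The documents give no value for b, s or ρ, so the gain cannot be put at a figure. The model does show that neither score is better than the other for a ratio outcome, and that the two together explain more whenever b is not zero and ρ is below 1.

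**4. Change in pain intensity.** For a later score Y, Y − P1 = (Y − P2) + (P2 − P1). The second bracket is complete before the study drug is given. With hypothetical scores of 6, 4 and 3, the change from the first request is 3 − 6 = −3, of which 4 − 6 = −2 came before the study drug and 3 − 4 = −1 after it. The bracket P2 − P1 has the same expectation in both arms, so it cancels from the between-arm difference on average but stays in each arm's reported change.

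**The case against.** The strongest reply is that Section 14.0 never fixes the first request. It says only 'baseline pain', and the label comes from the treatment sections. Section 14.0 gives each area its own starting time, so a baseline at each area's own request is a possible reading, at least for pain relief. Form 1 also records pain at rest and on movement before the PCA is stopped, a further candidate. The first-request score is a legitimate pre-drug covariate and the natural start of area A.

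Much of this stands. A reader might infer three stronger things that the documents do not support:

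- *That the first-request score is the only pain score called baseline.* Section 14.0 also gives that name to pain relief at an unspecified request.
- *That the first-request score is a wrong or weaker covariate, with a calculable loss.* Variance ratios built on a single post-drug score leave out area A. In the B/A model above, either score alone does equally well.
- *That the treatment contrast is biased or its size misstated.* The open-label dose is common to both arms and precedes the blinded drug.

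The reply does not show that the present wording is enough. The only label on pain intensity still points to the first request, and the score at the start of area B has no stated role in the model. Adding an effect-size figure for the change outcome would not help: if change is itself adjusted for the same baseline, the analysis is equivalent to adjusting the final score, and the plan does not say which is intended.

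**Conclusion.** The point holds as a free improvement to the analysis. By the protocol's own label, the covariate and the change outcome start one open-label dose before the randomised drug. This anchor is inferred from Sections 1.0 and 9.0, because Section 14.0 names no time.

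The choice of anchor introduces no bias and leaves the stated 80% power as it is. The loss has two parts: precision in the primary B/A comparison, of unknown size, and a within-arm change in pain intensity that combines two doses. The precision argument rests on a simple log-ratio model with equal slopes; if pain at request does not predict the AUC, there is nothing to gain. The validity check assumes complete data and does not model the removal rules in Section 13.0, which are a separate matter.

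**What to change.** In Section 14.0:

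- Fit the ANCOVA of B/A with two covariates, both on the 0-10 intensity scale: the first-request score (start of area A) and the score recorded immediately before the blinded study drug at the second request (start of area B, Form 2).
- Define change in pain intensity after study drug as measured from that second-request score, and state the time at which the change ends.
- Say which request is meant by baseline pain relief for each area.

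In Sections 1.0 and 9.0, rename the first-request score as pre-open-label pain intensity.

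Both scores are already collected and precede the study drug, so no visit, form or sample size changes. The only statistical cost is one degree of freedom: with 70 completers, 70 − 3 = 67 for one covariate becomes 70 − 4 = 66 for two. The change should be written in before unblinding.
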